1.2.2. Participant Populations for Analysis

Three participant populations will be defined:

Intent-To-Treat population (ITT population): Any participant randomized that received a dose of study drug and had post baseline VA data. ITT population are analyzed as they are randomized, regardless of which treatment a participant received.

Safety population (Safety population): Any participant randomized that received a dose of study drug. Safety population are analyzed based on the actual treatment received.

Per-Protocol population (PP population): Any participant who was randomized and received the protocol required study drug exposure and required protocol processing. Blinded clinical data will be reviewed prior to data lock to finalize the list of PP population.

The primary analyses will be performed in the intent-to-treat population. Analyses of efficacy endpoints in the PP population will provide supportive evidence. Safety summaries will be based on the Safety population.

1.2.3. Participant Disposition

Study completion and reasons for discontinuation for all randomized participants in the doubleblind phase will be summarized for each treatment group by simple tabulation. Discontinuations by reason will be tabulated by visit for each treatment group.

1.2.4. Demography and Other Baseline Data

Demographic data will be tabulated by treatment group. Past and current medical history will be summarized by treatment group using the system organ class (SOC) as coded using the Medical Dictionary for Regulatory Activities (MedDRA) coding dictionary.

1.2.5. Study Medication

Exposure and compliance will be tabulated by treatment groups.

1.2.6. Prior/Concomitant Therapy

Prior/concomitant therapy will be summarized.

Any medications or therapy present before the first dose of study medication will be considered as prior medications. Concomitant medications (medications present while on study medication) will be recorded throughout the study and at early discontinuation. These medications will be coded using the WHO-drug dictionary. The number of participants from the Safety Set using prior or concomitant medications will be categorized by the WHO-drug category and preferred term, and presented for each treatment group. In any given category (e.g., drug category) a participant will be counted only once.

1.3. Efficacy Data Analysis

1.3.1. Primary Outcome and Methodology

The primary endpoint is the percentage of vomiting as assessed by the VA questionnaire. The primary analysis method is CMH test adjusting for trips. The primary efficacy analysis will be based on the ITT population.

As there are two active doses, the higher dose 170 mg will be tested first. Vomiting rate in the 85 mg group will only be tested if the test in 170 mg group is positive.

The statistical analyses will be detailed in the statistical analysis plan (SAP).

1.3.2. Secondary Efficacy Analysis

The continuous secondary endpoints from NA as well as those from other questionnaires (MSAQ, PGI-S) will be analyzed by an analysis of variance (ANOVA) model with the main effects of treatment group and trip. The categorical secondary endpoints will be analyzed in the same way as the primary endpoint. Other statistical methods may also be used as deemed appropriate. The details will be provided in the SAP.

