- 2. To assess the effects of tradipitant 85 mg and 170 mg on the symptoms of motion sickness as measured by subjective parameter MSAQ.
- 3. To assess the effects of tradipitant 85 mg and 170 mg on the symptoms of motion sickness as measured by subjective parameter PGI-S.
- 4. To assess the safety and tolerability of a single oral dose of tradipitant 85 mg and 170 mg.

Overall Design: This is a randomized, double-blind, placebo-controlled trial to investigate the efficacy and safety of a single 85 mg or 170 mg oral dose of tradipitant in motion sickness affected male and female participants during vehicle travel.

The screening phase will consist of the participant taking the motion sickness eligibility questionnaire (MSEQ) to assess their susceptibility to motion sickness. Following this questionnaire, the participant will be interviewed to understand their history of motion sickness. If the participant meets pre-defined criteria as being eligible based on the motion sickness eligibility questionnaire and interview, they will proceed to the next step of a screening visit at a clinical site with a physician, and simultaneously, a lab visit for a blood draw. If the participant passes the medical visit screen and blood draw based on inclusion and exclusion criteria they will proceed to the evaluation phase.

Eligible participants will be randomized 1:1:1 to tradipitant 85 mg, 170 mg, or placebo. Eligible participants will be instructed to take tradipitant 85 mg, 170 mg, or placebo approximately 60 minutes prior to entering the boat. Boat travel will last approximately 120-300 minutes. The Vomiting Assessment (VA) and Nausea Assessment (NA) questionnaires will be completed approximately every 30 minutes of vehicle travel.

After the completion of the vehicle travel, the participant will complete the Patient Global Impression of Severity Questionnaire (PGI-S) and the Motion Sickness Assessment Questionnaire (MSAQ). All questionnaires will be submitted for analysis. Participants will then return for an EOS visit within 7 days of Visit 2.

Statistical Methods: Prevention of vomiting will be assessed by the VA, with the other questionnaires serving as secondary endpoints. The percentage of vomiting will be assessed by CMH test adjusting for the trips, and nausea severity measured by NA will be assessed by analysis of variance with the treatment group and trip as main effects. The primary efficacy analysis will be based on the ITT population.

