1. STATISTICS

1.1. Sample Size and Accrual

A sample size of 100 participants per arm (300 total) will provide around 96% power to detect a 26% difference in vomiting between tradipitant and placebo assuming 50% of participants on placebo will vomit and 24% of participants on tradipitant will vomit.

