1.2. Statistical Methods and Analysis Plan

1.2.1. General

This section describes the planned statistical analyses in general terms. A complete description of the methodology will be specified in a statistical analysis plan (SAP), which will be finalized prior to unblinding. Any changes in the statistical methods described in this protocol that occur prior to unblinding will be documented in the statistical analysis plan and will not require a protocol amendment.

Statistical hypothesis testing will be performed at two sided alpha level of 0.05 unless specified otherwise. For continuous variables, population size (N for sample size and n for available data), the mean, the standard deviation (SD), the median, the minimum and maximum values will be tabulated. For categorical variables, population size and frequencies in each category will be tabulated.

Multiplicity adjustments will be used to control study wise type I error at 5%. The details will be provided in the SAP.

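### Optional, nearly free improvement: the ANOVA for the continuous secondary endpoints is valid but adjusts only for treatment and trip; a scored MSEQ could be added, with a gain of unknown size

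*Combined protocol and SAP*

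**What the plan says.** Section 1.3.2 (Secondary Efficacy Analysis) says that the continuous endpoints from the NA, MSAQ and PGI-S "will be analyzed by an analysis of variance (ANOVA) model with the main effects of treatment group and trip". The synopsis, under Statistical Methods, names the same model for nausea: "nausea severity measured by NA will be assessed by analysis of variance with the treatment group and trip as main effects". Neither place names a participant-level baseline covariate.

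The synopsis, under Overall Design, describes screening as "the participant taking the motion sickness eligibility questionnaire (MSEQ) to assess their susceptibility to motion sickness". The same questionnaire, together with an interview, decides entry: "If the participant meets pre-defined criteria as being eligible based on the motion sickness eligibility questionnaire and interview", the person goes on to the medical and laboratory screen, and randomization comes after that. No items, score or cut-off for the MSEQ appear in the text available. The NA is completed during travel and the MSAQ and PGI-S after it; no pre-travel reading of any of the three is described.

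The plan also leaves room. Section 1.2.1 opens with "This section describes the planned statistical analyses in general terms", and section 1.3.2 adds "Other statistical methods may also be used as deemed appropriate. The details will be provided in the SAP". On changes of method made before unblinding, section 1.2.1 says that they "will be documented in the statistical analysis plan and will not require a protocol amendment".

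**The concern.** People differ in how prone they are to motion sickness, and that difference should carry over into nausea, MSAQ and PGI-S results. The trial measures susceptibility on everyone before randomization, yet the stated model does not use it. Whatever part of the outcome variation the MSEQ explains among enrolled participants therefore stays in the residual, and the confidence intervals for these endpoints may be wider than they need to be. Since no baseline version of the outcomes is described, the MSEQ is the natural candidate covariate.

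Only the precision of the continuous secondary endpoints is at stake. Bias, type I error and the primary analysis are not.

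**Working it through.** **1. The plan's own power figure.** Section 1.1 states that 100 per arm "will provide around 96% power to detect a 26% difference in vomiting between tradipitant and placebo", with rates of 50% and 24%. Null SE = √(2 × 0.37 × 0.63 / 100) = 0.0683; alternative SE = √(0.25/100 + 0.1824/100) = 0.0658.
- Pooled two-sided 5% test: Φ[(0.26 − 1.96 × 0.0683) / 0.0658] = 97.2%.
- With a continuity correction of 1/100: 96.1%. Fisher's exact test also gives 96.1%.

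The figure is reproduced. It concerns vomiting only. No effect size, SD or power is given for the continuous secondary endpoints, so no stated target depends on what follows.

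**2. Inputs.** From the documents: 300 participants, three arms of 100 (section 1.1 and synopsis), two-sided 5% level (section 1.2.1). Assumed: the number of trips T (10 to 30), and the within-arm, within-trip correlation r between the MSEQ score and the outcome among enrolled participants (0 to 0.5).

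**3. Formula.** Without the covariate, the error degrees of freedom are df0 = 300 − 3 − (T − 1). Adding one covariate multiplies the variance of a treatment difference by

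(1 − r²) × [1 + 1/(df0 − 2)].

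The first factor is the gain; the second is the price of estimating the slope. CI width changes by the square root of the product.

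- T = 10: df0 = 288, price 1/286 = 0.350%
- T = 20: df0 = 278, price 1/276 = 0.362%
- T = 30: df0 = 268, price 1/266 = 0.376%

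The trip count hardly matters. For T = 20:

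| Enrolled r | Variance factor | Change in CI width | 100 per arm is worth |
|---|---|---|---|
| 0 | 1.0036 | +0.2% | 99.6 |
| 0.1 | 0.9936 | −0.3% | 100.6 |
| 0.2 | 0.9635 | −1.8% | 103.8 |
| 0.3 | 0.9133 | −4.4% | 109.5 |
| 0.5 | 0.7527 | −13.2% | 132.9 |

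Break-even: r = √(1 − 1/1.00362) = 0.060 (0.059 for T = 10, 0.061 for T = 30).

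**4. Effect of the entry filter.** Selecting on the MSEQ narrows its range and so lowers r among those enrolled. For a normal score with only the top fraction eligible, let v be the remaining share of its variance. Then r(enrolled) = r√v / √(1 − r² + r²v). The fractions are assumptions.

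| Unselected r | Top half (v = 0.363): enrolled r, CI width | Top 30% (v = 0.265): enrolled r, CI width |
|---|---|---|
| 0.2 | 0.122, −0.6% | 0.104, −0.4% |
| 0.3 | 0.186, −1.6% | 0.160, −1.1% |
| 0.5 | 0.329, −5.4% | 0.285, −4.0% |

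**5. Validity and a check by simulation.** Both models were fitted to 4,000 simulated trials per setting (20 trips of 15, arms balanced within trips, r = 0, 0.2, 0.3, 0.5). With no treatment effect, rejection rates were 4.65% to 5.03% for the stated ANOVA and 4.60% to 5.00% with the covariate. The Monte Carlo SE is √(0.05 × 0.95 / 4000) = 0.34 points, so both models hold the 5% level. The mean SE changed by +0.18% (0.14118 to 0.14144), −1.8% (0.14119 to 0.13860), −4.4% (0.14148 to 0.13519) and −13.2% (0.14124 to 0.12256), as the formula predicts.

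**The case against.** The strongest reply is that there is little to report. Treatment plus trip is a standard, valid model; wanting one more covariate on secondary endpoints is a preference. The text available is a synopsis and a statistics section that describes itself as general, so its silence on covariates is to be expected. The MSEQ's scoring is not shown either: if it yields only eligible or not eligible, it is constant among randomized participants and cannot be used. The size of the gain rests on an assumed correlation.

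Much of this stands, and it sets the limits of the point. A reader might infer that the sponsor overlooked the covariate. The documents do not support that: the detailed SAP is not in the text available and may already include it. A reader might also infer that the planned ANOVA is biased or leaves these endpoints underpowered. Randomization protects the comparison, and the plan states no power for these endpoints that could be missed. Absolute power figures should not be quoted for them at all. Besides needing an effect size and SD that the plan does not give, they depend on whether arms are balanced within trips, which the synopsis does not state. In 20 trips of 15 without such balance, variance would be higher by a factor of about 15/14, or 7%.

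What the reply does not remove is the lopsided trade. A useless covariate widens intervals by about 0.2%, while any enrolled correlation above about 0.06 narrows them. The doubts about the SAP and the scoring are met by making the change conditional on both.

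**Conclusion.** The point holds as an optional efficiency gain, not as an error. It rests on two conditions: the MSEQ gives a numeric score that varies among randomized participants, and the detailed SAP does not already adjust for it.

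Its size cannot be settled from the documents. It is tempting to call it small, and the entry filter makes that plausible: an unselected correlation of 0.2 to 0.3 would leave a gain of 0.4% to 1.6% of CI width under the selection fractions tried. But nothing in the plan rules out a higher correlation, and at an enrolled value of 0.5 the gain would equal about a third more participants. The supportable statement is a range from a negligible loss to a moderate gain. The correlation, the trip count, the normal score and the eligible fractions are all assumptions; of these, only the trip count is shown not to matter.

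**What to change.** Unless the detailed SAP already does so, specify in the SAP or section 1.3.2 before unblinding:

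> Continuous secondary endpoints (NA, MSAQ, PGI-S) will be analyzed by ANCOVA with treatment group and trip as factors and the screening MSEQ score as a linear covariate. A missing score is replaced by the overall mean of the randomized participants, so that nobody is dropped.

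If the MSEQ has no numeric score, keep the stated ANOVA. Leave the primary CMH test adjusting for trips as it is.

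The cost is two sentences and one residual degree of freedom per model, with no new data and no further participants. Under section 1.2.1 a change made before unblinding needs no protocol amendment. Fixing the covariate in advance also keeps it from looking chosen after the results, which matters because section 1.3.2 leaves other methods open.

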1.4. Safety Data Analysis

1.4.1. Adverse Events

Adverse events will be recorded throughout the study and at early discontinuation. Adverse events and medical conditions will be coded using the Medical Dictionary for Regulatory Activities (MedDRA) coding dictionary. Treatment-emergent adverse events will be defined as those events, which are newly occurring or worsening from baseline. In all cases, only treatment emergent adverse events will be summarized.

VP-VLY-686-3401 Amendment 2 Confidential

Treatment-emergent adverse events will be summarized by presenting for each group the number and percentage of participants having any treatment-emergent AE, having an AE in each body system, and having each individual AE. (Note: In any given category [e.g. body system] a participant will only be counted once.) Similar displays will be provided for prior (conditions ending prior to the first dose of study medication) and current (conditions present while on study medication) medical conditions.

Adverse events will further be categorized by severity, relationship to study medication, and action taken. Other information collected will be listed, as appropriate. Any event starting more than 3 days after the final dose of study medication will be excluded from the above tables and only listed, unless the event caused discontinuation.

The proportions of participants experiencing SAEs and AEs resulting in discontinuation from the study will also be summarized.

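### The by-arm adverse event tables stop 3 days after the single dose although events are collected to the end-of-study visit, so up to 4 days of non-serious events get no by-arm count

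*Combined protocol and SAP*

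**What the plan says.** All of the relevant rules on adverse events are in Section 1.4.1 (Adverse Events) of the combined protocol and SAP.

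- Collection: "Adverse events will be recorded throughout the study and at early discontinuation".
- Definition: "Treatment-emergent adverse events will be defined as those events, which are newly occurring or worsening from baseline". The definition gives no end to the window.
- Tables: for each group, "the number and percentage of participants having any treatment-emergent AE, having an AE in each body system, and having each individual AE". Also, "Adverse events will further be categorized by severity, relationship to study medication, and action taken".
- Cut-off: events with onset later than "3 days after the final dose of study medication will be excluded from the above tables and only listed, unless the event caused discontinuation".
- After the cut-off sentence comes a separate summary: "The proportions of participants experiencing SAEs and AEs resulting in discontinuation from the study will also be summarized".

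The synopsis supplies the time frame. There is one dose, about an hour before the trip, so the final dose is the only dose. Under Overall Design, "Participants will then return for an EOS visit within 7 days of Visit 2". The fourth secondary objective is "To assess the safety and tolerability of a single oral dose of tradipitant 85 mg and 170 mg".

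**The concern.** The tables and the definition do not cover the same events. A non-serious event that starts on day 5 is collected and meets the plan's definition of treatment-emergent. Unless it led to discontinuation, it is missing from the overall TEAE row, from its body system, from its individual term, and from the splits by severity, relationship and action taken.

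The exception for discontinuation recovers little in this design. After day 3 the dose has been taken and the trip is over. A late event cannot stop treatment; it can only lead to withdrawal from the study before EOS.

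What is at stake is how the safety result is read. Someone who takes the overall TEAE percentage at face value would think it covers the period in which events were collected, when it covers the first 3 days. A comparison of arms over the later days would have to be counted by hand from the listing. The text gives no reason for choosing 3 days.

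**Working it through.** The plan gives no figure for the untabulated time, so there is none to reproduce.

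**Inputs**

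- Last onset day that is tabulated: day 3 after the only dose (Section 1.4.1; synopsis for the single dose).
- Latest EOS: day 7 after Visit 2 (synopsis, Overall Design).
- Participants: 100 per arm, 300 in total (Section 1.1).
- Assumption: Visit 2 is the dosing and trip day. The order of events in the synopsis implies this, but the text does not state it.

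**Formulas**

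Untabulated days = max(0, EOS day − 3). Share = untabulated days ÷ EOS day.

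| EOS day | Untabulated days | Share of days after dosing |
|---|---|---|
| 1 to 3 | 0 | 0% |
| 4 | 1 | 1/4 = 25% |
| 5 | 2 | 2/5 = 40% |
| 6 | 3 | 3/6 = 50% |
| 7 | 4 | 4/7 = 57% |

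If the dosing day itself is counted as follow-up, the share for day 7 is 4/8 = 50%.

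**Participant-days outside the tables**

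- Upper bound, every EOS on day 7: 100 × 4 = 400 per arm, and 300 × 4 = 1,200 in total.
- EOS spread evenly over days 1 to 7 (assumption): untabulated days sum to 0+0+0+1+2+3+4 = 10, so the mean is 10/7 = 1.43 days, or 100 × 10/7 = 143 per arm. The share is 10/(1+2+…+7) = 10/28 = 36%, or 10/35 = 29% if the dosing day is counted.
- EOS spread evenly over days 0 to 7 (assumption): 100 × 10/8 = 125 per arm.
- Lower bound, every EOS by day 3: 0.

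These figures measure time, not events. The document gives no late-event rate and no half-life, so the number of events left out cannot be estimated.

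**Which summaries are affected**

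The cut-off applies to the tables described above it. The sentence on serious events and discontinuations comes after it and carries no limit, so on a plain reading those proportions are complete. The laboratory, vital-sign and ECG summaries (Sections 1.4.2 to 1.4.4) are not touched. What remains uncounted is non-serious TEAEs with onset after day 3 that did not cause discontinuation.

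**The case against.** The strongest reply is that nothing here is an error. The cut-off is pre-specified, identical in all arms and stated openly. Section 1.4.1 can be read as one scheme, in which the definition opens the window and the 3-day sentence closes it for tabulation. A fixed window gives nearly equal observation time, whereas a table through EOS would vary with the visit date and pick up background events. Table titles and footnotes are not in the document and may well state the window. Section 1.2.1 calls the statistical section general and defers the complete methodology to a SAP, where a reason or a further table may exist. EOS within 7 days is an upper limit, so the gap could be zero for many participants. Late events are listed, and in a trial of about 300 participants counting them is a small task.

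Most of this stands, and it limits the weight of the point. A short window is legitimate, no bias between arms follows from it, and the participant-day totals illustrate an upper bound rather than show impact. It does not remove the point. Under either reading, the plan as written collects late non-serious TEAEs and provides no by-arm count of them, and a listing is not a count. If fuller SAP text already contains a through-EOS table, the point is resolved.

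**Conclusion.** The concern holds, at low severity. Followed exactly, Section 1.4.1 leaves 0 to 4 days of collected follow-up per participant without a by-arm count of non-serious TEAEs that did not cause discontinuation. At the latest permitted EOS this is more than half of the days after dosing. The range rests on Visit 2 being the dosing day; the averages rest also on an assumed spread of EOS days. The effect on any safety conclusion is unknown and may be small. This is a matter of reporting and labelling, not of the trial's validity.

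**What to change.** Keep the 3-day table and state in its title that it is restricted to onset within 3 days of the dose. Beside it, present by arm the number and percentage of participants with TEAEs from dose through EOS. Either may be called the main table. Footnote the through-EOS table with the median and range of the EOS day by arm, so that unequal observation time is visible.

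The cost is one extra set of displays from data already collected, with no new visits and no change to the efficacy analysis. Percentages in the added table will be slightly higher, some background events will be counted in all arms, and observation time will vary with the EOS date. Section 1.2.1 allows changes of statistical method made before unblinding to be recorded in the SAP without a protocol amendment.
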